Pilot Study of Natriuretic Versus Standard Doses of Mineralocorticoid Receptor Antagonists in
Heart Failure and Loop Diuretic Resistance in Outpatients

NCT: 02585843

Date 8/30/2015

Study Design

We conducted a pilot, prospective, single-center, double-blind, randomized, placebo controlled trial assessing the effects of high dose spironolactone in addition to intensified loop diuretic therapy vs. standard medical therapy in outpatients with ADHF. Our primary outcome was defined as weight change over the seven day study period. Based on data from a non-randomized intervention study, we aimed to recruit a total sample size of 40 subjects to detect a difference in our primary outcome of weight loss of 1.5kg difference between treatment and control.

On Day 1, all potential subjects were evaluated with complete medical history and physical examination, review of home medications, measurement of vital signs and body weight with a calibrated scale, serum collection for basic metabolic panel, liver function test, biomarkers of congestion, and electrocardiogram. "Imminent hospitalization" was determined by two independent HF specialists to assess the need for hospitalization for intravenous diuretics. Home MRAs were discontinued and potassium supplementation held if baseline serum potassium was >4.0mmol/L. Beta-blockers, ACE-I or angiotensin II receptor blockers were continued at home dose. Loop diuretic dosage was increased by two-fold. Patients were seen at two office visits in total, baseline at day 1 and final visit on day 7. On day 3, participants had serum basic metabolic panel to assess potassium levels and renal function for safety assessment.

Intervention

Enrolled patients were randomly assigned in a 1:1 ratio to high-dose (100mg/day) or standard-dose (25mg/day) spironolactone treatment groups.

Randomization, Allocation and Blinding

Randomization was stratified by sex and EF<45% in blocks of size 4. 2 by 2 randomization was performed via computer model generated by a study investigator. Allocations were concealed via the locked research pharmacy and the research team was blinded to treatment arm. All treatment medications were labeled in a blinded fashion. Subjects received 2 capsules per day (if standard dose: 25mg and placebo, if high dose: two 50mg) dispensed in vials of 2 capsules.

Study Endpoints

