Pilot Study of Natriuretic Versus Standard Doses of Mineralocorticoid Receptor Antagonists in
Heart Failure and Loop Diuretic Resistance in Outpatients

NCT: 02585843

Date 8/30/2015

Study Endpoints

The primary endpoint for the study was defined as change in total body weight at day 7 of the study period. Multiple secondary endpoints from day 1 to 7 were assessed. These included a) changes in dyspnea assessment scores; Visual Analogue Scale and 7-Likert scale, b) signs of congestion (i.e. JVP, peripheral edema and respiratory rales), c) 6MWT, d) serum and urinary creatinine, sodium, potassium and plasma aldosterone and renin activity and biomarkers of congestion and neurohormonal activation, e) furosemide equivalent of treatment loop diuretics doses, e) hospitalization at 30-, 60- and 90-days.

Six-minute walk test was performed per American Thoracic Society guidelines, along with Borg scores for dyspnea and fatigue at day 1 and 7. Serum and urinary creatinine, potassium, and sodium, plasma aldosterone and renin activity, and pro-BNP were assessed at days 1 and 7. Other biomarkers of peripheral congestion (CD146), inflammation (interleukin-6, tumor necrosis factor- α , endothelin-1) oxidative stress (isoprostane) and endothelial activation (vascular cell adhesion molecule-1) were assessed at day 1 and 7 and analyzed by ELISA or LC-MS.

A data monitoring committee of two independent cardiologists was established to evaluate safety, with a pre-specified stopping rule for harm but not for efficacy. Safety endpoints included changes in serum creatinine levels, eGFR, and the incidence of hyperkalemia during the 7 day treatment period. Safety was assessed by tracking adverse events including new or worsening renal dysfunction, and hyperkalemia. Serious adverse events were defined as death and all-cause hospitalization.

Statistical Analysis

Statistical analyses were performed using SPSS version 23. Continuous variables are presented as mean \pm SD (or median with IQR if not following normal distribution) and categorical variables were summarized as counts (percentages). The χ^2 test or Fisher's exact test (when cell counts were small) were used to compare categorical variables. Paired t-tests and the Wilcoxon rank sum test was used to compare continuous variables pre vs. post intervention within treatment arms. ANOVA was performed to compare continuous variables post-intervention. P< 0.05 considered statistically significant for all comparisons.

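### The SAP's one between-arm rule for continuous variables does not name the variable compared and omits the day-1 value and the stratification factors

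*SAP*

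**What the plan says.** The endpoint is a change. The SAP (Study Endpoints) states: "The primary endpoint for the study was defined as change in total body weight at day 7 of the study period". The Protocol (Study Design) agrees: "Our primary outcome was defined as weight change over the seven day study period". The same Protocol section aims for "a total sample size of 40 subjects to detect a difference in our primary outcome of weight loss of 1.5kg" between treatment and control. Body weight is taken on day 1: "measurement of vital signs and body weight with a calibrated scale". Randomisation is 1:1, stratified by sex and EF<45% (Protocol, Randomization, Allocation and Blinding).

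The SAP's Statistical Analysis section does not mention weight or the primary endpoint. It gives chi-square or Fisher tests to categorical variables. For continuous variables it has two sentences. The first concerns change within an arm: "Paired t-tests and the Wilcoxon rank sum test was used to compare continuous variables pre vs. post intervention within treatment arms". The second is the only candidate for comparing the arms: "ANOVA was performed to compare continuous variables post-intervention". That sentence names no response variable, baseline term or stratification factor. The Protocol contains no analysis model. On the other outcomes the SAP says: "Multiple secondary endpoints from day 1 to 7 were assessed".

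**The concern.** Two analyses fit the ANOVA sentence. One compares the arms on the change from day 1 to day 7, the other on the day-7 value alone. Both are unbiased under randomisation, but their precision can differ greatly. Body weight varies far more between patients than it moves in a week, so for weight the choice decides whether a 1.5 kg difference can be seen at all.

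For other variables measured on both days, the better of the two depends on the day-1 to day-7 correlation. A model that adjusts for the day-1 value has residual variance no larger than either. The stratification factors are left out under both readings, so the analysis does not follow the randomisation design.

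The surrounding text does not help to settle the wording. The preceding sentence gives the rank sum test, which is for two independent samples, to paired pre/post data.

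**Working it through.** **Inputs from the documents:** N = 40, 1:1 allocation, so 20 per arm; difference 1.5 kg; significance level 0.05. **Not given, so assumed:** two-sided testing, all SDs and all correlations.

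**1. The plan's own figure.** N = 40 cannot be reproduced, because SD, power and sidedness are not stated. Solving back (two-sample t, 20 per arm, two-sided 5%), N = 40 implies an SD of 1.86, 1.65 or 1.43 kg at 70, 80 or 90% power. An SD of that size describes a week's weight change rather than weight between patients, so the sizing fits a comparison of changes.

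**2. Weight under each reading.** Power comes from the noncentral t with df = 38 and noncentrality 1.5 / (SD × √(2/20)). The 95% CI half-width is t(0.975, 38) × SD × √(2/20).

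| Response | Assumed SD (kg) | Power for 1.5 kg | Half-width (kg) |
|---|---|---|---|
| Change | 1.5 | 87% | 0.96 |
| Change | 1.65 | 80% | 1.06 |
| Change | 2.0 | 64% | 1.28 |
| Change | 2.5 | 46% | 1.60 |
| Day-7 weight | 10 | 7.5% | 6.4 |
| Day-7 weight | 15 | 6.1% | 9.6 |
| Day-7 weight | 20 | 5.6% | 12.8 |
| Day-7 weight | 25 | 5.4% | 16.0 |

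**3. Does baseline adjustment add power for weight?** With weight SD 20 kg and change SD 1.65 kg, r = 1 − 1.65²/(2 × 20²) = 0.997. The adjusted residual SD is 20 × √(1 − r²), about 1.65 kg, the same as for change. Adding day-1 weight, sex and EF<45% takes residual df from 38 to 35. Counting df only, power goes from 80.0% to 79.8%. A simulation of 100,000 trials, with chance day-1 imbalance and no gain credited to sex or EF, gives 79.8% for change, 78.8% with day-1 weight added, 78.6% with sex and EF added as well, and 5.6% for raw day-7 weight. For weight, adjustment and change scores are practically equivalent.

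**4. Continuous secondary endpoints measured on days 1 and 7.** With equal day-1 and day-7 variances, relative to the day-7-only variance, the change score has 2(1 − r) and the adjusted model 1 − r². The ratio of adjusted to change is therefore (1 + r)/2. Equivalent N is 40 divided by the ratio.

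| Assumed r | Adjusted below day-7 only | Adjusted below change | N needed, day-7 only | N needed, change |
|---|---|---|---|---|
| 0.3 | 1 − 0.91 = 9% | 1 − 0.65 = 35% | 40/0.91 = 44 | 40/0.65 = 62 |
| 0.5 | 1 − 0.75 = 25% | 1 − 0.75 = 25% | 40/0.75 = 53 | 40/0.75 = 53 |
| 0.7 | 1 − 0.51 = 49% | 1 − 0.85 = 15% | 40/0.51 = 78 | 40/0.85 = 47 |
| 0.9 | 1 − 0.19 = 81% | 1 − 0.95 = 5% | 40/0.19 = 211 | 40/0.95 = 42 |

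The last two columns give the patients each unadjusted analysis would need to match the adjusted model with 40.

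**5. Rank sum on paired data.** For one arm of 20 with a true loss of 1.5 kg, weight SD 20 kg and change SD 1.65 kg (all assumed), pre versus post is significant in 0% of simulated trials by rank sum and 96% by signed-rank. Ignoring the pairing discards the information that the within-arm test needs.

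**The case against.** The strongest defence is that the documents already point to the right variable. Both define the primary endpoint as a change, and the sizing is for a difference in weight loss. The ANOVA rule covers continuous variables, and weight change is one. On that reading the SAP has a between-arm analysis for the primary endpoint, though a generic one, and it has adequate power if the change SD is near 1.65 kg. This stands.

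Three stronger readings are tempting, and the documents do not support them.

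- A reader might infer that the primary comparison has almost no power, or that 38 points (45.6 − 7.5) to 82 points (86.9 − 5.4) are being lost. That gap arises only if raw day-7 weight is compared, which is not the stated endpoint. It is not an expected loss.
- A reader might infer that the within-arm tests stand in for the treatment comparison. That would be unsafe: "Loop diuretic dosage was increased by two-fold" is part of the design for all patients, so both arms may lose weight whatever spironolactone does. But nothing in the SAP says the tests would be used that way.
- A reader might infer that omitting sex and EF<45% harms the weight analysis. Nothing in the documents shows that either predicts a 7-day weight change. Including them follows the randomisation; its benefit for weight is not demonstrated.

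It is also fair to say that the secondary-endpoint figures rest on assumed correlations, and that this is a pilot. What remains is that the response variable is unstated, the word *post-intervention* read literally favours day-7 values, and day-1 information already collected goes unused in the stated model.

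**Conclusion.** The point holds as a request to clarify, together with a nearly free gain in precision. For weight, ANOVA of change is the more natural reading and leaves little at stake; the collapse to 5-8% power is conditional on the literal day-7 reading and on weight SDs of 10-25 kg. For continuous day-1/day-7 secondary endpoints the loss is real under either reading. Its size depends on correlations that the documents do not give: small against change scores when r is high (5% at 0.9), large against day-7 values (81% at 0.9), and 25% against both at 0.5. Equal variances on the two days are assumed throughout. The rank sum test is misassigned as written, although this affects within-arm comparisons only.

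**What to change.** First, state which variable the between-arm ANOVA of weight used. If it was the change, one sentence settles the ambiguity for the primary endpoint.

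Then specify the between-arm analysis along these lines:

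> Seven-day weight change (equivalently, day-7 weight) is analysed in a linear model with treatment arm, day-1 weight, sex and EF<45%. The adjusted difference between arms in kg is reported with its 95% CI. Continuous secondary endpoints measured on days 1 and 7 use the same model with their own day-1 value; skewed biomarkers are log-transformed or analysed by ranks. Within-arm pre/post comparisons use the paired t-test or the Wilcoxon signed-rank test.

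For weight alone, ANOVA of change with sex and EF<45% is equally acceptable. Labelling the within-arm tests descriptive is optional.

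The SAP is written in the past tense. If the analysis has been run, keep the record of what was done and report the adjusted model as an added, labelled analysis.

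The cost is SAP wording and three degrees of freedom. For weight at a change SD of 1.65 kg, power goes from 80.0% to about 78.6%. No new patients or measurements are needed.

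### The only stated between-arm test for continuous endpoints neither adjusts for the day-1 value nor transforms skewed biomarkers; ANCOVA is a cheap, optional gain in precision

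*SAP*

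**What the plan says.** The SAP's Statistical Analysis section gives three kinds of test.

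- Categorical variables: chi-square or Fisher's exact test.
- Change within an arm: paired t-tests, and "Wilcoxon rank sum test was used to compare continuous variables pre vs. post intervention within treatment arms".
- Remaining continuous comparisons: "ANOVA was performed to compare continuous variables post-intervention".

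The last sentence does not name the groups. I read it as between arms because the sentence before it covers within-arm change. No covariate or transformation is mentioned. In the summaries, non-normality is handled by presentation: "or median with IQR if not following normal distribution". The 5% level is "considered statistically significant for all comparisons".

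Under Study Endpoints, day-1 values exist for the markers concerned: "plasma aldosterone and renin activity, and pro-BNP were assessed at days 1 and 7". CD146, interleukin-6, TNF-alpha, endothelin-1, isoprostane and VCAM-1 likewise "were assessed at day 1 and 7 and analyzed by ELISA or LC-MS". All of these are secondary. Weight, the primary endpoint, is defined as a change: "The primary endpoint for the study was defined as change in total body weight at day 7 of the study period". The Protocol (Randomization, Allocation and Blinding) stratifies by sex and EF<45%.

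**The concern.** Followed literally, a skewed marker would be summarized by its median but compared between arms on untransformed day-7 means, with the patient's own day-1 value set aside. In a trial where "we aimed to recruit a total sample size of 40 subjects", precision is scarce, and a baseline value already collected is the cheapest source of it.

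At stake is the chance of seeing a real biomarker effect and the width of its interval. The same sentence is also the only between-arm method for weight and the other continuous endpoints, so any rewording has to cover them too.

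**Working it through.** **The plan's own figure.** The only sample-size statement is 40 subjects for a 1.5 kg difference in weight loss (Protocol, Study Design). It gives no SD or power, so it cannot be reproduced. With 20 per arm and two-sided 5%, the implied SD is 1.5 / [(1.960 + 0.842) × √(2/20)] = 1.69 kg at 80% power, and 1.46 kg at 90%. Nothing is stated for any biomarker.

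**Inputs.** From the documents: 40 subjects, 1:1, hence 20 per arm, and the 5% level. Assumed: two-sided testing, distribution, log-SD, between-arm ratio and day-1/day-7 correlation ρ.

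**Variance factors**, relative to a day-7-only comparison when the SD is the same on both days: change score 2(1−ρ); ANCOVA 1−ρ².

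| ρ | 0.3 | 0.5 | 0.7 | 0.8 |
|---|---|---|---|---|
| Change score | 1.40 | 1.00 | 0.60 | 0.40 |
| ANCOVA | 0.91 | 0.75 | 0.51 | 0.36 |

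ANCOVA is the smaller at every ρ below 1.

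**Hand check on the log scale**, ratio 0.7, log-SD 0.5. The standardized effect is 0.357/0.5 = 0.713, and the test statistic is centred at 0.713/√(2/20) = 2.26. Normal-approximation power is Φ(2.26 − 1.96), about 62%. With ANCOVA at ρ = 0.7 the centre is 2.26/√0.51 = 3.16 and power is Φ(1.20), about 88%. Simulation with t-tests gives slightly less, as expected at 20 per arm.

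**Simulated power (%)**, lognormal, ratio 0.7, log-SD 0.5 (skewness 1.75); with 20,000 trials per setting the standard error is at most √(0.25/20,000), about 0.35 points:

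| Analysis | ρ 0.3 | 0.5 | 0.7 | 0.8 |
|---|---|---|---|---|
| ANOVA, day 7 | 55 | 55 | 55 | 55 |
| ANOVA, change | 35 | 44 | 63 | 79 |
| Log ANOVA, day 7 | 60 | 60 | 60 | 60 |
| Untransformed ANCOVA | 57 | 64 | 79 | 90 |
| Log ANCOVA | 62 | 71 | 86 | 95 |

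At this skewness most of the gain at higher ρ comes from the day-1 adjustment.

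**Other lognormal settings**, day-7 ANOVA / log ANOVA / log ANCOVA at the same four correlations:

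- Ratio 0.5, log-SD 1.0: 40 / 57 / 60, 68, 84, 94%. Untransformed ANCOVA reaches 59% at ρ = 0.7, so here the log scale matters. Both arms receive spironolactone and a doubled loop diuretic, so 0.5 is a large between-arm effect.
- Ratio 0.8, log-SD 0.5: 25 / 28 / 30, 35, 48, 62%.
- Ratio 0.8, log-SD 1.0: 8 / 11 / 11, 12, 16, 21%.

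Over log-SD 0.3–1.2 and ratio 0.5–0.8, adjustment on the log scale adds 0–3 points at ρ = 0.3, 0–11 at 0.5, 0–27 at 0.7 and 0–40 at 0.8. It costs up to 1.5 points at ρ = 0.

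**Unfavourable case for the log scale.** Gamma marker, skewness 2.0, ratio 0.5. Day-7 ANOVA has 51–52%.

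| Analysis | ρ 0.3 | 0.5 | 0.7 | 0.8 |
|---|---|---|---|---|
| Log ANCOVA | 42 | 49 | 63 | 78 |
| Rank ANCOVA | 47 | 54 | 68 | 81 |
| Untransformed ANCOVA | 53 | 60 | 74 | 87 |

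**Type I error** with no effect, lognormal settings: ANOVA 3.3–5.3%, log ANCOVA 4.7–5.3%, rank ANCOVA 4.5–5.3%.

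**Weight.** If raw day-7 weights were compared and their SD were 10 to 25 kg (assumed), the statistic for 1.5 kg would be centred at 1.5/(10 × √(2/20)) = 0.47 down to 1.5/(25 × √(2/20)) = 0.19. Power would be only about 7% down to 5%.

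**The case against.** The strongest reply is that this is a preference. Randomization makes a day-7 comparison unbiased, type I error is not inflated, the biomarkers are secondary endpoints of a pilot sized only on weight, and every input to the power figures is assumed. All of that stands. It limits the point to an optional improvement but does not remove it, because the covariate is already collected.

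Second, the comparator is uncertain. The ANOVA sentence does not say whether values or changes are compared, and the endpoints are framed from day 1 to day 7. If changes were meant, the day-1 value is used, and the gains differ: smaller than against day-7 values at high correlation, larger at low. ANCOVA is still ahead in the settings run (at ρ = 0.7: 63% for change, 79% and 86% for the two ANCOVAs). Likewise, the rank-sum test is a two-sample test placed in a paired sentence. If it was meant between arms, the scale gap nearly closes (54–55% against 57% for log ANOVA at ratio 0.5, log-SD 1.0), but day-1 values remain unused.

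Third, the log scale is not shown to be best for every marker. The gamma case bears this out: log ANCOVA trails untransformed ANCOVA at every correlation and the existing ANOVA at ρ = 0.3. Day-1 adjustment is the firmer half of the recommendation.

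A reader might infer that the primary analysis has only 5–7% power. The documents do not support that. Weight is defined as a change, and at 80–90% power the planned 40 subjects imply an SD of about 1.5–1.7 kg, which fits a change better than weights between patients. The wording fails to exclude a raw day-7 comparison; it does not prescribe one.

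**Conclusion.** The point holds as an optional improvement. As stated, the between-arm method specifies no baseline adjustment and no scale for skewed markers. The loss is in precision, and the documents do not fix its size: with the assumed lognormal marker at ratio 0.7 and log-SD 0.5, log ANCOVA adds about 7 points of power over day-7 ANOVA at correlation 0.3 (62 − 55) and about 40 at 0.8 (95 − 55).

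These figures assume 20 analysable patients per arm, two-sided 5% and lognormal data, which favour the log scale. The strata terms were not simulated. It would be wrong to conclude that the biomarker comparisons are biased or over-reject, or that logging always helps.

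**What to change.** Replace the ANOVA sentence in the SAP with:

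> Continuous variables measured on days 1 and 7, including weight, are compared between arms by ANCOVA of the day-7 value adjusted for the day-1 value and the randomization strata (sex, EF<45%). The concentration biomarkers pro-BNP, aldosterone, renin activity, CD146, IL-6, TNF-alpha, endothelin-1, isoprostane and VCAM-1 are analysed on the log scale on both days and reported as geometric mean ratios with 95% CI, with rank ANCOVA as the one sensitivity analysis for every biomarker.

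This keeps the weight endpoint as defined: with day 1 in the model, the arm effect on day-7 weight equals the arm effect on change. Logging also needs a rule for values below the detection limit. Setting them to half the limit lowered log ANCOVA power from 84.0% to 81.5, 77.4 and 73.2% with 10, 20 and 30% of day-1 values affected (lognormal, ratio 0.5, log-SD 1.0, ρ = 0.7), with type I error at 4.9–5.1%.

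The cost is two sentences and a log transform in SPSS, with no new data. Residual degrees of freedom fall from 38 to 35 (40 − 5: intercept, arm, day-1 value, two strata). Biomarker effects become ratios, the gain from adjustment is close to nil at low correlation, and the log scale can lose up to about 10 points against the existing ANOVA if logged values are left-skewed (gamma case, ρ = 0.3). The SAP is written in the past tense. If the data have already been analysed, label the ANCOVA post hoc.

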The primary endpoint for the study was defined as change in total body weight at day 7 of the study period. Multiple secondary endpoints from day 1 to 7 were assessed. These included a) changes in dyspnea assessment scores; Visual Analogue Scale and 7-Likert scale, b) signs of congestion (i.e. JVP, peripheral edema and respiratory rales), c) 6MWT, d) serum and urinary creatinine, sodium, potassium and plasma aldosterone and renin activity and biomarkers of congestion and neurohormonal activation, e) furosemide equivalent of treatment loop diuretics doses, e) hospitalization at 30-, 60- and 90-days.

Six-minute walk test was performed per American Thoracic Society guidelines, along with Borg scores for dyspnea and fatigue at day 1 and 7. Serum and urinary creatinine, potassium, and sodium, plasma aldosterone and renin activity, and pro-BNP were assessed at days 1 and 7.

Other biomarkers of peripheral congestion (CD146), inflammation (interleukin-6, tumor necrosis factor- α , endothelin-1) oxidative stress (isoprostane) and endothelial activation (vascular cell adhesion molecule-1) were assessed at day 1 and 7 and analyzed by ELISA or LC-MS.

A data monitoring committee of two independent cardiologists was established to evaluate safety, with a pre-specified stopping rule for harm but not for efficacy. Safety endpoints included changes in serum creatinine levels, eGFR, and the incidence of hyperkalemia during the 7 day treatment period. Safety was assessed by tracking adverse events including new or worsening renal dysfunction, and hyperkalemia. Serious adverse events were defined as death and all-cause hospitalization.

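### Does the plan need a named analysis set and a missing-weight rule before the day-7 weight comparison can be relied on?

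*SAP*

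**What the plan says.** The primary endpoint is set out in the Study Endpoints section of both documents: "The primary endpoint for the study was defined as change in total body weight at day 7 of the study period".

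The SAP's Statistical Analysis section gives two procedures for continuous outcomes. Within arms: "Paired t-tests and the Wilcoxon rank sum test was used to compare continuous variables pre vs. post intervention within treatment arms". Between arms: "ANOVA was performed to compare continuous variables post-intervention". It names no analysis population, imputation or sensitivity analysis.

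The protocol's Study Design section fixes when weight can be observed: "Patients were seen at two office visits in total, baseline at day 1 and final visit on day 7". The contact between those visits is described only as a blood test: "On day 3, participants had serum basic metabolic panel to assess potassium levels and renal function for safety assessment".

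On size, the same section says "we aimed to recruit a total sample size of 40 subjects to detect a difference in our primary outcome of weight loss of 1.5kg". It gives no SD, power or allowance for losses.

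On events that could remove a patient before day 7, Study Endpoints says "Serious adverse events were defined as death and all-cause hospitalization". Neither event is linked to the weight analysis.

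**The concern.** A paired test and an ANOVA on post-treatment values both need a day-7 weight. A patient who dies or misses the final visit has no post-baseline study weight and drops out. The analysed set is therefore decided by events after randomisation, and the text does not say so.

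Losses are plausible. These are outpatients with decompensated heart failure, and two specialists assessed at entry whether admission was close. The protocol does not say whether patients judged to be in that position were enrolled.

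If lost patients responded worse than average, three things could follow:

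- The between-arm difference moves in favour of whichever arm lost more of them.
- The within-arm weight loss is overstated in any arm that lost such patients.
- Each loss takes power from a target that has no stated margin.

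**Working it through.** **Inputs.** From the documents: a 1.5 kg difference, 40 patients allocated 1:1 (20 per arm), and a 0.05 significance level. Assumed, because the documents give nothing: a two-sided test, the numbers lost, the SD, the arm means, and *d*, the amount by which a lost patient's weight loss falls short of the arm average (1, 2 or 3 kg). The ANOVA is taken as applied to weight change.

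**1. Can the target of 40 be reproduced?** No, because SD and power are missing. Solving for the SD at which 20 per arm just suffices:

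- Normal approximation, 80% power: 1.5 × √10 / (1.960 + 0.842) = 1.69 kg. The noncentral t gives 1.65 kg.
- At 90% power: 1.46 kg, or 1.43 kg by noncentral t.

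Whether 40 contains slack depends on the unstated SD. At 80% power by the normal approximation, an SD of 1.5 kg needs 16 per arm (32 in total, 8 spare). An SD of 2.0 kg needs 28 per arm (56 in total, so 40 falls short).

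**2. Power if some patients are not weighed** (noncentral t, 40 taken as exactly sufficient):

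| Weighed | SD 1.65 kg | SD 1.43 kg |
|---|---|---|
| 40 | 80.0% | 90.0% |
| 38 | 77.8% | 88.4% |
| 36 | 75.5% | 86.6% |
| 32 | 70.1% | 82.1% |

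**3. Shift in the between-arm difference.** If *k* of 20 are lost from an arm, the mean loss among those weighed rises by *kd*/(20 − *k*). With *kc* lost from control and *kh* from high dose, the shift is *d* × [*kh*/(20 − *kh*) − *kc*/(20 − *kc*)]. This needs no SD and no arm mean. For 3 control and 1 high dose, 1/19 − 3/17 = −0.124, so the shift is −0.124*d*.

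The last column applies the natural candidate for a sensitivity analysis, setting each missing change to 0 kg, with assumed arm losses of 1.0 kg (control) and 2.5 kg (high dose): [50 − *kh*(2.5 − *d*)]/20 − [20 − *kc*(1 − *d*)]/20.

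| Lost (control, high dose) | Weighed patients only, *d* = 1, 2, 3 | Missing set to 0 kg, *d* = 1, 2, 3 |
|---|---|---|
| 1, 0 | 1.45, 1.39, 1.34 | 1.50, 1.45, 1.40 |
| 3, 1 | 1.38, 1.25, 1.13 | 1.43, 1.33, 1.23 |
| 2, 2 | 1.50, 1.50, 1.50 | 1.35, 1.35, 1.35 |
| 1, 3 | 1.62, 1.75, 1.87 | 1.28, 1.38, 1.48 |

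The true value is 1.50 kg throughout. The standard error with 20 per arm is 1.65 × √(2/20) = 0.52 kg, so the largest shift is 0.37/0.52 = 0.7 of a standard error.

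**4. False-positive rate** with no true difference and a 3, 1 split. The standard error is 1.65 × √(1/17 + 1/19) = 0.551 kg. The shift is 0.22, 0.45 or 0.67 standard errors, and the nominal 5% becomes about 5.5%, 7.2% or 10%.

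**5. Within-arm shift**, 2 of 20 lost: 2*d*/18 = 0.11, 0.22 or 0.33 kg, against a standard error of 1.65/√20 = 0.37 kg. An arm that loses nobody does not shift.

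**The case for a change.** The best case for a change is that the remedy costs a few sentences and could matter with 20 per arm. A two-patient imbalance can move the estimate by 0.37 kg, a quarter of the 1.5 kg target, and could double the false-positive rate. The within-arm tests are more exposed, because an even split does not cancel there. Naming the analysed set in advance would also remove any suspicion that it was chosen after the results were seen.

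Part of this stands. The omissions are real, no redaction explains them, and the directions of bias are right for any arm that loses worse-responding patients. Numbers randomised, weighed, admitted, dead and missing by arm would let a reader settle the question. Those counts belong in the report of results. Admissions and deaths are already recorded as serious adverse events, and hospitalisation is also a secondary endpoint, so supplying them does not depend on a different analysis.

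The rest is weaker. No loss rate is documented. The 0.37 kg and the 10% need a 3 to 1 split within seven days and *d* = 3 kg, which is 3/1.65 = 1.8 assumed SDs; with an assumed control loss of 1.0 kg, those control patients would have gained 2 kg on average. At *d* = 1 kg the false-positive rate is 5.5%. The within-arm tests do not address the 1.5 kg comparison for which the trial was sized.

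**Conclusion.** No change to the plan is needed. This is missing detail that analysts would fill sensibly: compare the observed day-7 weights of all randomised patients, by assigned arm. Writing that down would label the primary comparison without altering it, and if every patient was weighed no result would move.

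The one new calculation on offer is not an improvement. Setting missing changes to 0 kg pulls the estimate to 1.35 kg at an even split, where the default is unbiased. At a 3, 1 split it differs from the biased estimate by only 0.05 to 0.10 kg, so it would reassure when it should warn. At a 1, 3 split it can land near the truth (1.48 kg) or well below it (1.28 kg), depending on *d*. Filling in a constant also understates the variance.

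On sample size, the absence of a stated allowance does not show that 40 is too few, since SD and power are not given. Losing 2 to 4 patients would cost about 2 to 5 points of power from 80%, which is modest for a pilot.

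These sizes rest on assumed loss counts, *d*, SD and arm means. The conclusion rests on less: only day-1 and day-7 weights are described, no imputation is stated, and the natural reading already gives the analysis that a written rule would name. Substantial and lopsided losses would call for cautious interpretation of the result.
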